102        items, each on a 4-point Likert scale. Each item is scored as 0 (can't do at all), 1  
103        (much difficulty), 2 (with some difficulty), or 3 (no difficulty). The item scores  
104        are then summed to determine the subscale score out of 60 (no difficulty for all  
105        items). Resultant scores for each subscale are divided by the total range from 0-  
106        100 with 0 as greatest disability and 100 as no disability. The PSS has  
107        demonstrated good test-retest reliability (ICC2,1 = 0.94) with a SEM90 of 8.5.  
108        The MDC90 is 12.1, and the minimal clinically important difference (MCID) was  
109        found to be 11.4.

110        *American Shoulder and Elbow Surgeons (ASES) Shoulder Score*

111        The American Shoulder and Elbow Surgeons (ASES) Shoulder Score,  
112        originally published in 1994 and validated in 2002, is a self-report  
113        questionnaire consisting of two sections: one visual analog scale (VAS) to

114 measure pain, and ten items to measure activities of daily living. The  
115 questionnaire takes 3 minutes to complete and is scored as follows: [(10 – VAS  
116 pain) x 5] + (5/3 x sum of ADL items). Resultant scores for each subscale range  
117 from 0-100 with 0 as greatest disability and 100 as no disability. The ASES has  
118 demonstrated good to excellent test-retest reliability (ICC = 0.61-0.96) with an  
119 SEM of 6.7. The MDC95 is 11.2, and the MCID was found to be 12.0. A  
120 recent systematic review found the ASES to be one of the only patient-reported  
121 functional scales for rotator cuff disease to have measurement error below 10% of  
122 the global score.

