PENN SHOULDER SCORE/ASES SHOULDER SCORE Part II: Function: Please circle the number that best describes the level of difficulty you might have performing each activity.		No difficulty	Some difficulty	Much difficulty	Can't do at all	Did not do before injury
1. Reach the small of your back to tuck in your shirt with your hand.	3	2	1	0	X	
2. Wash the middle of your back/hook bra. (ASES #3)	3	2	1	0	X	
3. Perform necessary toileting activities. (ASES #4)	3	2	1	0	X	
4. Wash the back of opposite shoulder.	3	2	1	0	X	
5. Comb hair. (ASES #5)	3	2	1	0	X	
6. Place hand behind head with elbow held straight out to the side.	3	2	1	0	X	
7. Dress self (Including put on coat and pull shirt over head. (ASES #1)	3	2	1	0	X	
8. Sleep on affected side. (ASES #2)	3	2	1	0	X	
9. Open a door with affected side.	3	2	1	0	X	
10. Carry a bag of groceries with affected arm.	3	2	1	0	X	
11. Carry a briefcase/small suitcase with affected arm.	3	2	1	0	X	
12. Place a soup can (1-2 lbs.) on a shelf at shoulder level without bending elbow.	3	2	1	0	X	
13. Place a one gallon container (8-10 lbs.) on a shelf at Shoulder level without bending elbow.	3	2	1	0	X	
14. Reach a shelf above your head without bending your elbow. (ASES #6)	3	2	1	0	X	
15. Place a soup can (1-2 lbs.) on a shelf overhead without bending your elbow.	3	2	1	0	X	
16. Place a one gallon container (8-10 lbs.) on a shelf Overhead without bending your elbow. (ASES #7)	3	2	1	0	X	
17. Perform usual sport/hobby. (ASES #8)	3	2	1	0	X	
18. Perform household chores (cleaning, laundry, cooking).	3	2	1	0	X	
19. Throw overhand/swim/overhead racquet sports. (circle all that apply to you) (ASES #8)	3	2	1	0	X	
20. Work full-time at your regular job. (ASES #10)	3	2	1	0	X	
SCORING: (office use only)	PSS	PSS	PSS	PSS	PSS	
PSS Total of all columns = _____ (a)	_____	_____	_____	_____	_____	
Number of "X's" x 3 = _____ (b), 80 - _____ (b) = _____ (c)	_____	_____	_____	_____	_____	
(If no "X's" are circled, function score = total of columns)	ASES	ASES	ASES	ASES		
PSS Function Score = _____(a) + _____(c) = _____ x 80 = _____ of 80	_____	_____	_____	_____		
ASES Score = _____						
Total of shaded columns: _____ x 5/3 = _____ of 60						

[figure not shown]
Physical Therapy at St. Lukes - Physical Therapy at St. Luke's - West End  
INTAKE FUNCTIONAL STATUS SUMMARY

Patient:	Risk-Adjustment Criteria			
ID#:			Gender:	
Date of Birth:			Comorbidities:	
Initial DOS:			Payer:	
Body Part:		Severity:		
Impairment:		Age:		
Surgery Type:		Acuity:		

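### The ASES function rule makes no allowance for activities the patient never did, so applied as written they count as total inability; the form corrects this for the PSS only

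*Combined protocol and SAP*

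**What the plan says.** Section C, under the ASES Shoulder Score, describes a pain scale to "measure pain, and ten items to measure activities of daily living". The score is a pain term plus a function term, in the formula ending "pain) x 5] + (5/3 x sum of ADL items", and is said to run "from 0-100 with 0 as greatest disability and 100 as no disability". The text does not mention items that do not apply to the patient.

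The ASES items are collected on the combined Penn/ASES form in Appendix C (Part II). All 20 items, including the ten tagged ASES, offer scores 3 to 0 and a fifth response, X, headed "Did not do before injury". The scoring block treats the two scales differently:

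- **PSS:** it begins "Number of 'X's' x 3 = _____ (b" and subtracts that product from the maximum. It adds "If no 'X's' are circled, function score = total of columns", so the plain total is meant only for forms without X's.
- **ASES:** the whole instruction is "Total of shaded columns: _____ x 5/3".

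Section D gives no rule for X or blank items on either scale. In Section C the PSS function score is also a plain sum; its X correction appears only on the form.

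**The concern.** An X says the activity was not part of the patient's life before the injury. It says nothing about the shoulder. Yet an X has no numeric value and adds nothing to a plain sum, as a 0 for complete inability does. The form recognises this for one of two scores built from the same answers and leaves the other uncorrected.

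X answers are foreseeable. Section B admits adults with no upper age limit and no requirement about work or sport, and the ASES set includes a sport or hobby item (17), an overhead sport item (19) and a full-time job item (20). The exclusion of patients who cannot complete the questionnaires does not help, because an X is a completed answer.

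Aim 2 compares patient-reported function across irritability levels, and the ASES is one of its three scales. Under the rule as written, the ASES partly reflects employment and sporting habits, and can disagree with the PSS for the same patient on the same answers.

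**Working it through.** **Inputs.** From Section C: ten ASES items, function = 5/3 × sum, total range 0–100, MDC95 11.2, MCID 12.0. From the form: items scored 0–3, or X with no number. Mean item scores and X frequencies are not in the documents; values used for them below are assumptions.

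**The plan's own range.** Maximum = (10 − 0) × 5 + 5/3 × (10 × 3) = 50 + 50 = 100. Minimum = (10 − 10) × 5 + 0 = 0. The stated range reproduces, and each function item is worth 5/3 × 3 = 5 points.

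**Loss per patient.** Let k items be X and let the other 10 − k have mean m.

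- As written: 5/3 × (10 − k) × m.
- Prorated over answered items, the logic of the form's PSS rule: 50 × (10 − k)m / [3 × (10 − k)] = 50m/3.
- Difference: 5/3 × k × m.

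| X answers (k) | m = 1 | m = 1.5 | m = 2 | m = 2.5 | m = 3 |
|---|---|---|---|---|---|
| 1 | 1.67 | 2.5 | 3.33 | 4.17 | 5.0 |
| 2 | 3.33 | 5.0 | 6.67 | 8.33 | 10.0 |
| 3 | 5.0 | 7.5 | 10.0 | 12.5 | 15.0 |

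Two cases with X on items 17, 19 and 20:

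- Full marks on the other seven: 5/3 × 21 = 35, against 50 × 21/21 = 50.
- A score of 2 on the other seven: 5/3 × 14 = 23.3, against 50 × 14/21 = 33.3.

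**PSS on the same answers.** With those three X's and full marks on the other 17 items, the form's rule gives 51/(60 − 9) × 60 = 60 of 60. This reads the denominator as 60, as in Section C. PSS function is then perfect while ASES function is 35 of 50.

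**Group level, X's even.** The as-written score is (10 − k)/10 of the prorated score. If every patient had the same k, and m did not depend on which items were X, ASES function differences between groups would shrink by k/10: 10% for one X, 30% for three. If k varies between patients but not systematically by group, it also adds noise.

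**Group level, X's uneven.** Suppose one group has a larger share of patients with three X's at m = 2. An excess of 10, 20 or 30 percentage points moves that group's mean by 0.1 × 10 = 1, 0.2 × 10 = 2 or 0.3 × 10 = 3 points. These shares are illustrative only.

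**The case against.** The strongest reply is that the plan is silent rather than wrong. Nowhere does it say that X equals 0; scorers might leave the item or the score missing, or prorate as for the PSS. The scoring block was also damaged in extraction (stray totals of 80 and 60, lost shading), and any missing-item rule in the source cited for the ASES cannot be seen. It is true that X = 0 is inferred. But it is what the stated sum produces, and shading cannot alter that because X carries no number. If staff did something else, that too would be unspecified and could vary between scorers. The stray figures are not used as evidence here.

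A reader might infer that a retired, non-sporting patient loses 15 points, more than the cited MDC95 and MCID. The documents do not support that as a typical case. Fifteen needs X on all three items and full marks on the other seven, in someone attending for shoulder pain. Item 17 also covers hobbies, so such a patient may have only two X's and lose at most 10. With three X's the loss passes 11.2 only if m exceeds 11.2/5 = 2.24, and 12.0 only if m exceeds 12.0/5 = 2.4. Both are thresholds for change, whereas Aim 2 compares group means at one time, so they give scale and no more.

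Two further objections stand. Section C's prose omits the X rule for the PSS as well, so the gap in the text is not confined to the ASES. And proration assumes skipped items are about as hard as answered ones; if overhead sport and full-time work are harder, the prorated score is somewhat too high.

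**Conclusion.** The point holds as a scoring defect in one of Aim 2's three scales. Followed as written, the ASES rule lowers the score for activities the patient never did. The loss is at most 5 points per X, 7.5 to 10 for three X's at an assumed mean item score of 1.5 to 2, and at most 15 for three X's.

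Uneven X's across irritability groups would bias the ASES comparison. Even X's would shrink or blur differences, since better-functioning patients lose more per X; that works against the hypothesis of Aim 2. It would go too far to conclude that the Aim 2 result is biased by a known or clinically important amount: the documents give neither X frequencies nor their spread over groups. The PABAK-OS reliability analysis in Aim 1 does not use the ASES score, and FOTO is administered as a separate computerized test, so neither is affected.

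**What to change.** In Section C, with a matching sentence in Section D:

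1. Score ASES function as 50 × (sum of answered ASES items) / (3 × number of ASES items answered).
2. State the X rule for PSS function in the text, so that protocol and form agree.
3. Fix, before analysis, a maximum number of X or blank items beyond which the score is missing. The number is the sponsor's choice; the documents give no basis for a particular one.
4. Report the unprorated ASES as a sensitivity analysis. Tabulating X counts by irritability group would show whether bias or shrinkage is the more likely effect.

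The cost is a few sentences and a scoring change on item answers the form already captures, with no added patient burden. The downsides are a departure from the plain formula and some possible inflation of function if the skipped items are harder than the answered ones. The sensitivity analysis shows how much the choice matters.

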#### 123 Numeric Pain Rating Scale

124 The Numeric Pain Rating Scale (NPRS) is an 11-point Likert scale that can be  
125 used to measure pain intensity. The NPRS is a standard pain assessment scale that uses a  
126 0-10 scale (no pain to worst pain imaginable, respectively) in order to determine a  
127 patient's level of pain. Patients rate their current level of pain and their worst and least  
128 amount of pain in the last 24 hours. The average of the 3 ratings is used to represent the  
129 patient's level of pain. The NPRS has demonstrated good reliability (ICC2,1=0.74) and  
130 responsiveness (MDC = 2.5, MCID = 1.1) in subjects with shoulder pain and excellent  
131 reliability in an upper extremity orthopaedic population. Furthermore, the NPRS has  
132 been used to assess pain severity of both traumatic and atraumatic etiologies.

#### 133 Range of Motion

134 Goniometric measurements of shoulder AROM in symptomatic patients  
135 demonstrates fair-good reliability with regards to intra- and inter-rater reliability (Inter-  
136 rater Rho = 0.64-0.80; Intra-rater Rho = 0.53-0.91). Passive range of motion (PROM)  
137 demonstrates even greater reliability with intra-examiner ICC values = 0.98, and inter-  
138 examiner ICC values ranging from 0.87-0.89.

#### 139 End Feel - Pain

140 The ability to utilize end feel to determine sequence of pain in relation to tissue  
141 resistance has generally shown good intra-rater reliability (K = 0.48 to 0.59, Kw = 0.59  
142 to 0.87) and is frequently used for clinical decision-making.

#### 143 Procedures

144 At least 2 raters will be recruited from each site. Raters will be trained with the following  
145 materials: (1) Collaborative Institutional Training Initiative (CITI) training for those involved in  
146 consenting the patients; (2) the reading of the Staged Approach for Rehabilitation Classification:  
147 Shoulder Disorders with direction to pay special attention to the section on Level 3  
148 classification and Table 3;6(pp 795-6) and (3) a short online narrated presentation to reinforce  
149 understanding of the content. The intent of this training method is to increase the generalizability  
150 of the study results, and to avoid overly specialized training methods that would be difficult to  
151 reproduce clinically.

152        Patients will be recruited by the raters from their regular caseload (Appendix C). Patients  
153 will receive a brief explanation about the study, provide informed consent, and be asked to  
154 complete the functional questionnaires as part of the outpatient admissions process. The first  
155 therapist will rate the patient's shoulder symptom irritability level during the normal examination  
156 process utilizing the intake (Appendix C). Raters will inquire on the presence of night or resting  
157 pain and complete a physical examination including measurement of active and passive shoulder  
158 flexion. Range of motion measurements will be utilized for direct comparison and to determine  
159 the onset of pain during passive motion. Shoulder flexion will be measured utilizing goniometric  
160 procedures described elsewhere. Active range of motion testing will be performed in  
161 standing and passive range of motion testing will be performed in supine.

162        After the first rater has completed their examination and prior to any intervention that  
163 may change the shoulder symptom irritability, a second rater, blinded from the first rater's  
164 assessment, will then examine and rate the subject (Appendix C). In addition to the shoulder  
165 symptom irritability rating, both raters will also be asked to provide a treatment intensity  
166 recommendation based upon the examination findings (Appendix C). Data collection forms will  
167 be placed in a sealed envelope and sent via interoffice mail for analysis. To maintain rater  
168 blinding, raters will be asked to not discuss ratings until data collection is complete.

#### 169 ***Data Collection and Storage***

170        Data will be collected for a period of 6 months. All data will be kept on a secure,  
171 password-protected server (RedCap, Nashville, TN; <https://redcap.slhn.org/>).

#### 172 ***Section D: Statistical Analysis***

173        Descriptive statistics will be used to characterize both raters and patients. Frequencies  
174 will be utilized for categorical variables, and means with standard deviations for continuous  
175 variables.

176        A repeated measures design, utilizing two raters per subject, will be utilized to determine  
177 inter-rater reliability. The raters will independently rate the subject's shoulder symptom  
178 irritability level utilizing the recently developed shoulder symptom irritability scale. The inter-  
179 rater reliability will be evaluated using the PABAK-OS statistic. For evaluation of statistical  
180 significance, a two-tailed confidence interval will be utilized with  $\alpha$  set to 0.05, and the null  
181 hypothesis will be that the PABAK-OS will be  $<0.40$ .

182        Analysis of variance with post-hoc analysis will be utilized for evaluation of differences  
183 in patient reported functional limitation and pain subscales between shoulder symptom  
184 irritability groups. For evaluation of statistical significance,  $\alpha$  will be set to 0.05.

185        Lastly, to evaluate correlation between intervention intensity and diagnosed level of  
186 shoulder symptom irritability, the PABAK-OS statistic will be used. Additionally, independent t-  
187 tests will be utilized to evaluate for difference between groups for hypotheses 1 and 2 of aim 3.  
188 For evaluation of statistical significance,  $\alpha$  will be set to 0.05.

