### 3 **Section A: Experimental Design**

4 This study will employ a quasi-experimental design utilizing repeated measures (specific  
5 aim 1), followed by cross-sectional analysis (specific aims 2 and 3). The target sample size for  
6 the study will be 25 physical therapists and 90 patients. Patient-reported outcome measures were  
7 selected based upon their reliability, validity and internationally accepted use. Given that there is  
8 no single universal patient reported outcome measure for the shoulder, multiple measures will be  
9 utilized during the third aim of this project.

#### 10 Specific Aim 1

11 The first specific aim will be to determine the reliability of the shoulder symptom  
12 irritability classification scale. To address this aim, the project will analyze paired rater  
13 judgments of shoulder symptom irritability (high, moderate or low) from 90 patients with  
14 shoulder pain. Raters will be physical therapists from multiple clinics trained in rating shoulder  
15 symptom irritability. Prevalence-adjusted, bias-adjusted Kappa for ordinal scales (PABAK-OS)  
16 will be the primary measure of reliability. However, analysis may be adjusted based on the data  
17 distribution.

#### 18 Specific Aim 2

19 The second aim is to compare level of functional limitation between shoulder symptom  
20 irritability groups. To address this aim, the project will analyze patient-reported functional  
21 measures using analysis of variance with post-hoc analysis to compare functional disability  
22 across different levels of shoulder symptom irritability. The independent variable will be the  
23 shoulder symptom irritability level, and dependent variables will include patient-reported  
24 functional status measures. The hypothesis is that patients with higher irritability will report  
25 greater functional deficits.

#### 26 Specific Aim 3

27 The final specific aim is to determine if the level of shoulder symptom irritability dictates  
28 the chosen intervention intensity. To address this aim, raters will select planned intervention  
29 choices for each of the 90 patients, utilizing a pre-specified list of possible physical therapy  
30 interventions. Data analysis will include PABAK-OS for correlation, and independent t-test for  
31 differences between clinical specialist and non-specialist groups. The hypothesis is that patients  

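### Aim 3 assesses the correlation of irritability with intervention intensity by PABAK-OS, a matching index whose value does not by itself show association

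*Combined protocol and SAP*

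**What the plan says.** Section A, Specific Aim 3, poses the question: "The final specific aim is to determine if the level of shoulder symptom irritability dictates" the intensity chosen. It predicts that high irritability goes with interventions that keep tissue stress low, and low irritability with more intense ones. Its analysis sentence reads "interventions. Data analysis will include PABAK-OS for correlation, and independent t-test for" and continues "differences between clinical specialist and non-specialist groups. The hypothesis is that patients".

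Section D repeats the target, "Lastly, to evaluate correlation between intervention intensity and diagnosed level of", and the statistic, "shoulder symptom irritability, the PABAK-OS statistic will be used". It adds that independent t-"tests will be utilized to evaluate for difference between groups for hypotheses 1 and 2 of aim 3". The supplied text lists no numbered hypotheses for Aim 3.

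Alpha for Aim 3 is 0.05. The only null value for the index is in the inter-rater reliability paragraph of Section D: "hypothesis will be that the PABAK-OS will be" below 0.40. The full name, "Prevalence-adjusted, bias-adjusted Kappa for ordinal scales (PABAK-OS"), appears under Aim 1. The supplied text gives no weights. The sentence allowing the analysis to change with the data distribution also belongs to Aim 1.

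Section C, Procedures, has both raters give an irritability rating and a treatment-intensity recommendation, and refers to Appendix C. That appendix holds a three-level, select-one strategy form and a separate list of six treatment items with yes/no, two-option and three-option answers. Section E restricts Aim 3 to patients on whom the raters agree completely.

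**The concern.** Whether two ratings fall on the same level and whether one rises with the other are different questions. PABAK-OS addresses the first. Its chance term comes from equal category use, not from the observed splits. Its value therefore mixes any relation between irritability and intensity with how often each level happens to be used.

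This can mislead in both directions. If most patients are rated moderate and most are given the middle strategy, the index can be clearly positive when therapists ignore irritability. If therapists follow irritability strictly but one step away from the matching level, the index can be low. In either case the result would be reported under the word correlation, and a reader given only the index could not tell which situation applied.

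**Working it through.** **Plan figure.** The documents give no expected value, null or sample size for this Aim 3 analysis. Their one sample-size figure, 48, is for the reliability kappa (0.80 against 0.40, 80% power). A standard two-rater binary kappa formula reproduces it at an assumed prevalence of 0.30, but it does not bear on this point.

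**Inputs from the documents.** Three irritability levels; three strategy levels (Appendix C); 90 patients; Aim 3 limited to agreed patients; kappa 0.80 (Section B).

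**Assumptions.** The splits and the weights, since neither is given. Number of agreed patients: if 0.80 is read as an unweighted PABAK, raw agreement is 0.80 x 2/3 + 1/3 = 0.867, and 90 x 0.867 = 78.

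**Formula.** PABAK-OS = (po - pe) / (1 - pe). Here po is the weighted observed agreement and pe is the mean of the 3x3 weight matrix: 1/3 unweighted, 5/9 linear, 2/3 quadratic. Adjacent levels get weight 0, 0.5 or 0.75. High irritability is matched with minimised stress.

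**Worked case: independent, both 20/60/20.** Exact matches: 0.04 + 0.36 + 0.04 = 0.44. Adjacent cells: 4 x 0.2 x 0.6 = 0.48.
- Unweighted: (0.44 - 0.333) / 0.667 = 0.16
- Linear: (0.44 + 0.24 - 0.556) / 0.444 = 0.28
- Quadratic: (0.44 + 0.36 - 0.667) / 0.333 = 0.40

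**Other independent cases** (unweighted / linear / quadratic):

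| Irritability; intensity | PABAK-OS |
|---|---|
| Equal thirds; equal thirds | 0 / 0 / 0 |
| Equal thirds; 10/80/10 | 0 / 0.175 / 0.35 |
| 10/80/10; 10/80/10 | 0.49 / 0.595 / 0.70 |
| 60/10/30; 60/10/30 | 0.19 / -0.01 / -0.215 |
| 60/30/10; 10/30/60 | -0.185 / -0.305 / -0.425 |

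There is no association in any row.

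**Perfectly monotone one-step shift, equal thirds.** High irritability always gets the middle strategy; moderate and low always get the most intense one. One-third match exactly and two-thirds are adjacent.
- Unweighted: (0.333 - 0.333) / 0.667 = 0
- Linear: (0.333 + 0.333 - 0.556) / 0.444 = 0.25
- Quadratic: (0.333 + 0.5 - 0.667) / 0.333 = 0.50
- Tau-b: of the three pairs of irritability groups, two are concordant and one is tied on intensity, so tau-b = 2 / sqrt(3 x 2) = 0.82

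Tau-b in turn hides that two-thirds of patients miss the matching level. Each measure shows what the other conceals.

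**How often a 95% interval would mislead.** 40,000 simulated samples per setting, no association, n = 78, Wald interval (unweighted / linear / quadratic):

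| Split | Interval above 0 | Interval above 0.40 |
|---|---|---|
| Both equal thirds | 2% / 3% / 4% | 0% / 0% / 0% |
| Both 25/50/25 | 11% / 47% / 66% | 0% / 0% / 0.1% |
| Both 20/60/20 | 48% / 93% / 98% | 0% / 0.1% / 5% |
| Both 10/80/10 | 100% / 100% / 100% | 24% / 82% / 99% |

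For both 20/60/20, moving n between 66 and 90 changes the first column only to 46-51% / 89-96% / 95-99%. With opposite-end clustering (60/30/10; 10/30/60) the interval lies wholly below 0 in 73% / 89% / 87%.

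**The case against.** The strongest reply is that the Aim 3 hypothesis is itself about matching. It pairs high irritability with low stress and low irritability with higher intensity, and the strategy form mirrors the three irritability levels. On that reading a concordance index fits, and a low score for a one-step shift is correct behaviour. This stands, and it is a reason to keep PABAK-OS. It does not make the index a measure of correlation, which is the word used in both Section A and Section D.

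The large false-signal rates rest on assumed middle clustering and on a null of 0. No passage predicts 60-80% of patients in the middle level, and against 0.40 the rates are small except under strong clustering. This also stands. But 0.40 is stated for Aim 1 only, so the plan cannot be credited with that protection.

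The cited source for the index may fix the weights, and the unlisted hypotheses may add comparisons. Neither can be checked here, so the point is limited to what the supplied text describes.

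Three stronger readings are tempting and are not supported:
- That the index always exceeds 0 when both variables cluster in the same level. With both at 60/10/30 the weighted forms are at or below 0.
- That the study would probably report a false correlation. The documents give neither the splits nor the null needed to say so.
- That no form supplies the intensity variable. Appendix C offers two candidates; the plan does not choose between them.

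**Conclusion.** The concern holds in a limited form. The only described analysis relating irritability to intensity is a matching index whose zero does not mean no association, so its value alone cannot support a statement about correlation. This is a property of the index and needs no assumption about the data.

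The size does rest on assumptions. Across the splits tried, the index under no association ranges from -0.425 to 0.70, depending on the weights. The practical risk runs from negligible at equal thirds to serious when both variables gather in the middle level, and depends on a null that Aim 3 lacks. The choice of PABAK-OS as a concordance measure is not at fault. What is missing is a companion measure of association and the details that make the index interpretable. This should be fixed before analysis.

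**What to change.** In Section D, for Aim 3:

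1. Name one ordinal association measure as the test of correlation, for example Kendall tau-b against 0, with a confidence interval that allows for clustering by rater. The interval method is the sponsor's choice, provided it is stated in advance.
2. Show the 3x3 table of irritability by strategy.
3. Report PABAK-OS beside it as the concordance measure, with its weights stated, and with its null if it is to be tested.
4. State that the three-level strategy item in Appendix C is the intensity variable for this table, and which rater's choice is paired with the agreed irritability level. The yes/no and two-option items in the treatment list cannot form a 3x3 table; if analysed, they need methods suited to their own scales.

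The cost is revised wording, one added statistic and one table. No new data or patients are required.
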